Adverse Events were summarized for all reported data and by study period: a) up to and including 28 days post last dose of initial treatment.

Efficacy Analyses: The primary efficacy endpoint of disease control rate (DCR), defined as the sum of complete, partial and stable disease responses divided by the total number of subjects in the efficacy population, will be determined per criteria based on RECIST or iRECIST. DCR was tabulated overall and by subgroups of interest.

For DCR, exact binomial 95% confidence intervals will be computed using the Clopper-Pearson method. Median time to response and duration of response will be summarized for those subjects with responses, using the Kaplan-Meier method; overall survival (OS) will be similarly summarized. Individual tumor measurements, tumor burden, % changes in tumor burden, and progression free survival (PFS) will be listed.

Changes in overall survival will be presented graphically for all monotherapy subjects, for monotherapy subjects receiving an INT230-6 dose volume over the course of their treatment less than or \geq 40% of their incoming reported total tumor burden, with pembrolizumab, with ipilimumab and in all sarcoma types (collectively) for monotherapy and combined with ipilimumab.

Pharmacokinetic Analyses: The pharmacokinetic analyses described will be reported in a separate report. A brief summary of the results will be included in this CSR. The release kinetics of each analyte is not expected to be uniform across subjects. Sponsor shall assess the blood concentrations of the three analytes for each subject at the first cycle. Sponsor shall correlate the systemic measurement [maximum plasma drug concentration (C_{max}), area under the curve (AUC)] of the 3 analytes to measured markers of systemic toxicity [in particular renal and blood – the known toxicities of the two active agents; cisplatin (CIS) & vinblastine (VBL)]. Human plasma will be analyzed for the concentration of VBL and 8-((2-hydroxybenzoyl)amino)octanoate (sodium salt form) (SHAO) using validated LC/MS/MS methods, and for cisplatin using a validated ICP-MS method. For pharmacokinetic profiling platinum drugs, total platinum levels in subject plasma or urine are routinely determined by spectroscopy methods as a surrogate. Thus an ICP-MS method will be developed for this study to measure total platinum in human samples as a surrogate for cisplatin.

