7.5. Examination of Subgroups

Analysis endpoints of safety and efficacy variables may be further explored with the following subgroups:

- Tumor ratio (1:4, 1:3, 1:2 or dose set by longest diameter formulas)
- Dose schedule (every 2 weeks versus every 4 weeks)
- Superficial tumor injection subjects versus deep tumor injection subjects
- Tumor type (Sarcoma)
- Status of prior treatment with platinum-based antineoplastics or vinca alkaloid therapies
- Subjects with less than 2 tumors injected compared to those with ≥ 2 tumors
- Tumor burden: subjects receiving $\geq 40\%$ of tumor burden injected versus those receiving $< 40\%$; tumor burden is calculated based on EDC documentation of target, bystander, non-target, and new tumors. Subjects receiving $\geq 40\%$ of baseline total tumor burden injected overall (during the course of therapy) and at first dose will be explored. For overall, the sum of all injection volumes will be used in the calculation.

The subgroups to be analyzed for each endpoint are described in Section 8, Section 9, and Section 10.

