Individual tumor assessments for target and bystander, non-target, and new lesions will be listed, with location, method of assessment, longest diameter, shortest diameter, depth, volume, and percent change from baseline included for each target and bystander tumor, as well as Total Tumor Burden at Baseline, Cumulative Dose, Percent TTB dosed, and dose category (< 40% versus \geq 40%) per subject. Another listing will be produced for the Abscopal effect of bystander tumors, defined as any bystander tumor with any decrease in tumor size at any point during the study, but before being injected with study drug.

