9.2. Progression-Free Survival and Overall Survival

Progression free survival (PFS) and Overall Survival (OS) will be evaluated for the All Treated Population, the REP, and the SEP. PFS will be defined as the time (in months) from first dose of INT230-6 to either observation of clinical deterioration, removal from study, or occurrence of death due to any cause within 126 days (approximately 2 time intervals for tumor assessments) of the last tumor assessment. Progression date will be defined as the end of treatment date as captured per eCRF guidelines when the reason for end of treatment is either 'Radiographic

deterioration' or 'Clinical deterioration.' In subjects without a progression date or with a death date more than 126 days after the last tumor assessment, the PFS time will be censored on the date of last tumor assessment or last treatment date if the subject has no post-baseline tumor assessments. PFS analyses will consider tumor assessments after treatment discontinuation.

OS will be defined as the time (in months) from first dose of INT230-6 to death. Subjects for whom death is not reported will be censored at the date of end of study.

PFS and OS will be summarized in a listing. The median time to OS as obtained from Kaplan-Meier methods will be tabulated by subgroup and will include the median, 25th percentile, 75th percentile, and a 2-sided point-wise 95% confidence interval. Hazard ratios may be determined between certain curves for the Kaplan Meier figures noted below.

A Kaplan Meier figure of OS for the All Treated, REP, and SEP populations will be presented for each of the following:

- a curve all treated monotherapy patients, a curve for subjects that received a dose to total tumor burden < 40% of tumor burden, a curve for those subjects that had a dose to total tumor burden \geq 40%,
- a curve for escalation cohort combining A1, B1, EA, EC, and a curve for escalation cohort combining EC2 and EC3,
- a curve for sarcoma patients in the monotherapy cohort and a curve for monotherapy sarcoma patients having \geq 40% of their total tumor burden treated,
- a curve for the pembrolizumab DEC/DEC2 combined cohort for subjects,
- a curve for all ipilimumab FEC cohort subjects,
- a curve for the ipilimumab FEC sarcoma subjects, a curve for all monotherapy sarcoma patients and a curve for monotherapy sarcoma subjects having \geq 40% of their total tumor burden treated will be included.

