1. TOTAL TUMOR BURDEN (TTB)

Step 1: If all 3 dimensions are reported, volume = (longest*shortest*depth*0.63)

Step 2: If not all 3 dimensions are reported and longest diameter is reported, volume calculation is based on the longest diameter measurement.

1. If $. < \text{longest} < 1.5 \text{ cm}$, volume = 1 cm^3
2. If $1.5 \leq \text{longest} \leq 4 \text{ cm}$, volume = $\text{longest}^3/2$
3. If $4 < \text{longest} < 9 \text{ cm}$, volume = $\text{longest}^3/3$
4. If $\text{longest} \geq 9 \text{ cm}$, volume = $\text{longest}^3/4$
5. If shortest is only measurement reported, Diameter = shortest and follow step 2 tasks 1 to 4 for volume calculations

Step 3: Sum all calculated volume values across target and bystander tumors.

2. % DOSED TTB

Step 1. Calculate TTB of all of a patient's bystander and target tumors reported in the database using the TTB formulas above.

Step 2. Calculate patient's cumulative dose of INT230-6

Step 3. Calculate % Dosed TTB as (cumulative dose / Patient TTB) * 100.

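### Overall survival runs from first dose, but the 40% dose groups are formed by dose accumulated afterwards, which biases the ≥40% curve toward benefit

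*SAP*

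**What the plan says.** **Clock.** SAP 9.2: "OS will be defined as the time (in months) from first dose of INT230-6 to death".

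**Curves.** SAP 9.2 requires Kaplan-Meier OS figures in the All Treated, Response Evaluable and Scan Evaluable Populations. They include "a curve for subjects that received a dose to total tumor burden" under 40%, its counterpart at 40% or more, and curves for monotherapy sarcoma subjects with at least 40% of their burden treated. Hazard ratios are optional.

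**Grouping variable.** The SAP Synopsis plans the figures "for monotherapy subjects receiving an INT230-6 dose volume over the course of their treatment less than or" at least 40% of the reported incoming burden. Appendix 1, item 2, gives the rule: "Calculate % Dosed TTB as (cumulative dose / Patient TTB) * 100". SAP 9.1 lists, per subject, tumor data "as well as Total Tumor Burden at Baseline, Cumulative Dose, Percent TTB dosed, and dose category". SAP 7.5 names subjects with at least 40% "of baseline total tumor burden injected overall (during the course of therapy) and at first dose will be explored", and sums all injection volumes for the overall version.

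**Denominator.** SAP 7.5: "tumor burden is calculated based on EDC documentation of target, bystander, non-target, and new tumors". Appendix 1, item 1: "Sum all calculated volume values across target and bystander tumors".

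**Duration of dosing.** Under Protocol 12.1.3.1, dosing falls on days 0, 28, 56, 84 and 112 in A1/B1 and on days 0, 14, 28, 42 and 56 in the E cohorts. The Protocol Synopsis adds maintenance every 9 weeks for up to 2 years in EC3. Protocol 12.1.6 ends treatment at progression or clinical deterioration.

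**Safeguards.** SAP 7.8 plans no covariate adjustment. Neither document plans a landmark or time-dependent analysis of these curves.

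**The concern.** Group membership is decided after time zero, by an exposure that a subject must survive and stay on treatment to accumulate. A subject who dies or deteriorates early has few sessions and tends to land below 40%. A subject who reaches 40% has, by construction, survived to the session at which that happened. The curves would therefore separate even if dose did nothing.

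The research hypothesis in SAP 3.1 is that treating enough of the visible disease prolongs survival, and this split is the figure that speaks to it most directly. An artefact could be read as support. The sarcoma curves have the same problem if they use the same measure, which the SAP does not state. The A1/B1/EA/EC versus EC2/EC3 curves are grouped by cohort and are not affected.

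**Working it through.** **1. The SAP's own example.** The documents give no effect size or event count for this comparison. The only figure to reproduce is the worked percentage in Appendix 1 (Other Notes). TTB = 22.68 + 1.89 + 1.26 + 1.134 = 26.964 cc, and (20 + 2)/26.964 = 81.6%, against about 81.5% stated. The cumulative rule is confirmed. (The example's text gives 1 mL for the second tumor but adds 2 mL; with 1 mL the result is 21/26.964 = 77.9%.)

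**2. Earliest day 40% can be reached by ratio.** Minimum sessions = 0.40/ratio, rounded up, with the whole burden injected at full load.

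| Cohort | Ratio | Per session | Sessions | Earliest day |
|---|---|---|---|---|
| A1, B1 | 1:4 | 25% | 2 | 28 |
| EA | 1:4 | 25% | 2 | 14 |
| EC2, EC3 | 1:3 | 33.3% | 2 | 14 |
| EC | 1:2 | 50% | 1 | 0 |

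In EC the 30 mL first-dose limit allows this only if TTB ≤ 30/0.40 = 75 cc and at least 0.40/0.50 = 80% of it is injected. In the other cohorts, a ratio-dosed subject who dies before the second session is in <40% by construction. Longest-diameter dosing (Protocol 5.2) may give more per session; its table is redacted.

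**3. Volume limits (Protocol Tables 4–7b).** In A1 the cumulative limit is 5 + 10 + 15 = 30 mL at day 56, 45 mL at day 84 and 60 mL at day 112. A 100 cc subject is at most at 30% on day 56 and first passes 40% on day 84 (45%). Above 60/0.40 = 150 cc, 40% is out of reach. At full load in EC2 or EC3 the same 100 cc subject has 2 × 33.3 = 66.7 mL, or 67%, by day 14.

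**4. Deaths in that window.** With exponential survival and median m months, the share dead by day d is 1 − 2^(−d/(30.4375·m)). For days 14/28/56/112 this gives 5/10/19/35% at an assumed median of 6 months, 3.5/7/13/25% at 9 months and 2.6/5/10/19% at 12 months.

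**5. Null simulation (no dose effect).** From the protocol: ratios, dosing days and total-volume limits by cohort. Assumed:
- equal cohort sizes, and median OS of 6, 9 or 12 months
- lognormal TTB with median 15, 60 or 150 cc and log-SD 1
- 20–100% of TTB injected per session, fixed per subject
- 24 months of follow-up
- survival exponential, Weibull (shape 1.5), or with no deaths in the first 8 weeks

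Dose per session = min(limit, ratio × share injected × TTB). Tumor shrinkage and retreatment were not modelled. Each scenario had 30,000–40,000 subjects and a Cox model.

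| HR, ≥40% vs <40% | Dosing until death | Dosing stops at 30–90% of survival time |
|---|---|---|
| As written, all scenarios | 0.40–0.92 | 0.34–0.76 |
| As written, no deaths in first 8 weeks | 0.82–0.92 | 0.52–0.76 |
| As written, alive at 2 months (Scan Evaluable) | 0.83–0.99 | 0.54–0.85 |
| Week-12 landmark | 0.98–1.04 | 0.76–0.96 |
| Day-70/126 landmark | 0.96–1.05 | 0.72–0.91 |

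Example (true median 9 months, median TTB 60 cc, dosing until death): median OS 10.3 vs 3.1 months, HR 0.54, with exponential survival; 9.3 vs 7.7 months, HR 0.86, with no deaths in the first 8 weeks. Uneven cohort mixes extended the low end to 0.28. Placing all burden in one tumor gave 0.33–0.96; raising the EC3 dose by half, as a stand-in for longest-diameter dosing, gave 0.36–0.96. Other assumptions about the injected share gave still lower values, some with almost nobody below 40%; no weight is put on those.

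**6. False positives.** The number of monotherapy subjects is not given. With an assumed 40, 60 or 80 (median 9 months, TTB 60 cc), two-sided p<0.05 favoring ≥40% appeared in 10–84% of null trials, against a nominal 2.5% and 4–12% with the week-12 landmark.

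**7. Cross-check.** A separate, simpler simulation used five sessions of 4–25% of TTB each, unrelated to prognosis, with exponential survival. With dosing until death the HR was 0.58–0.71 for 14-day and 0.42–0.58 for 28-day dosing. Stopping 28 or 60 days before death gave 0.39–0.57 and 0.34–0.45. All 18 scenarios favored ≥40%.

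**The case against.** **A baseline split may already be planned.** SAP 9.2 tabulates median OS by subgroup, and SAP 7.5 mentions a first-dose 40% split, which is known at the start of follow-up. It does avoid the bias. But SAP 7.5 says only that subgroups may be explored, SAP 9.2 does not assign this split to the figures, and outside EC few subjects dosed by ratio could be in the upper group.

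**The denominator is clearer than it looks.** The Appendix 1 example uses baseline target and bystander tumors, and three other places say baseline or incoming. This stands: a fixed denominator is the natural reading, so growth of the denominator in longer survivors is unlikely to offset the bias. The conflict over tumor classes between SAP 7.5 and Appendix 1 remains.

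**Early deaths may be few.** Eligibility requires a life expectancy of at least 8 weeks (Protocol 6.1), and the Scan Evaluable Population requires a scan at two months or later. Both reduce the bias. The first is a forecast, however, and even taken literally leaves 0.82–0.92 or 0.52–0.76. If the qualifying scan is taken as week 12, the Scan Evaluable range becomes 0.92–1.00 with dosing until death and 0.65–0.87 with earlier stopping.

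**The largest effects rest on assumed stopping.** This also stands. Protocol 5.2.1 and 9.3 allow treatment through unconfirmed progression, and the week-12 scan follows every-2-week induction, so stopping before day 56 would be mainly clinical. For those cohorts on five doses, with no death or stop before day 56, the HR is 0.99–1.04: no bias.

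**OS is exploratory.** True, and no decision rule depends on these curves. That limits the seriousness; it does not make the figure interpretable.

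**Conclusion.** The concern holds. Time zero is first dose, the groups are formed by later cumulative dose, and nothing in the plan corrects for it. Confidence is high on direction. The size cannot be taken from the documents: under the stated assumptions the null HR lies roughly between 0.3 and 0.95, depending mainly on early mortality, on when dosing stops and on the cohort mix. It should be fixed before the 40% curves are interpreted. Because OS is exploratory and hazard ratios are optional, it does not undermine the trial's primary safety conclusions.

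**What to change.** 1. Make the dose-group OS comparison, and any hazard ratio from it, a prespecified landmark analysis. Group subjects alive at the landmark by percent dosed TTB received by then, and time OS from the landmark. The week-12 scan (SAP 4.4) is a natural choice. About day 70 for every-2-week and day 126 for monthly dosing is an alternative that counts the A1/B1 day-112 dose. Adjust for log baseline TTB where numbers allow: if TTB is prognostic (assumed HR 1.22–1.49 per log unit), the week-12 null HR is 0.69–1.00 unadjusted and 0.81–1.02 adjusted.
2. Keep the from-first-dose 40% curves, if at all, as descriptive figures labelled as subject to immortal-time bias.
3. State one measure: which tumors make up TTB, that it is fixed at baseline, and whether the sarcoma curves use cumulative dose over TTB.
4. For the Scan Evaluable Population, start the clock at the qualifying scan or state that survival to it is guaranteed by definition. This matters mainly for absolute medians and for scattered scan dates; it barely changes a group hazard ratio if scans occur at similar times.

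**Cost.** SAP wording and some programming, with no new data. Deaths before the landmark drop out: 6–28% of subjects at week 12, or 5–30% at day 70/126, under the assumed survival. The week-12 version omits the A1/B1 day-112 dose. Some bias remains where dosing stops for deterioration (0.76–0.96 at week 12). If few subjects are below 40% at the landmark the comparison is uninformative, and TTB adjustment may be unstable in the sarcoma subset. The apparent benefit will shrink.

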10. SAFETY ANALYSES

The primary safety objective is to assess the safety of INT230-6 in subjects with advanced or recurrent malignancies as determined by the rate of \geq Grade 3 AE's attributed to INT230-6 and not the underlying disease. Safety and tolerability of INT230-6 will be assessed for the All Treated Population. Adverse events will be graded using the National Cancer Institute's Common Terminology Criteria for Adverse Events Version 4.03. Dose limiting toxicities (DLT) for this study are defined as a \geq Grade 3 study drug-related adverse events occurring during the first dose (DLT window extends up to 28 days after dosing), with exceptions noted in Section 9.1.1 of the study Protocol.

Subjects will be monitored throughout the treatment and follow-up period for occurrence of AEs. Additional safety parameters to be measured/assessed include PE findings, vital sign measurements, hematology, coagulation, serum chemistries, urinalysis, ECOG performance status, and ECG.

Tables related to the safety analyses are located in Section 14.3 and listings in Section 16.2.

10.1. Adverse Events

Adverse event summaries will be based on treatment-emergent adverse events (TEAEs), and will be presented by study part. TEAEs are defined as any non-serious AE or unrelated serious AE (SAE) that occurs during or after administration of the first dose of treatment through 28 days after the last dose, any non-serious AE or unrelated SAE that occurs during or after retreatment up to 28 days post-dose of the last re-treatment, any related SAE occurring after first dose of treatment without respect to date of last dose, or any event that is present at baseline but worsens in intensity. Adverse events will be summarized by treatment. Events worsening in severity will be considered new AEs. AEs recorded in the eCRF that began prior to treatment will be recorded and displayed as part of the medical history.

All adverse events will be coded using Version 25.1 of MedDRA. Summaries of TEAEs will present data by System Organ Class (SOC) and preferred term (PT) in order of decreasing frequency of total SOC count, followed by decreasing frequency of total PT count. The following conventions will be followed in summarizing multiple occurrences of an adverse event for a certain assessment period when summarizing data from individual subjects:

- Each subject will be counted only once within SOC or PT
- The highest known severity within a body system or a PT will be assigned to the event
- The strongest relationship within a body system or a PT will be assigned to the event.

The denominator used for calculation of percentages will be the number of subjects in the All Treated population per cohort.

An overall summary of treatment emergent adverse events (TEAEs) will include:

- number and percentage of subjects with one or more TEAEs
- number and percentage of subjects with one or more INT230-6 monotherapy TEAEs
- number and percentage of subjects with one or more TEAEs for DEC and DEC2 cohorts (not by individual drug agent)
- number and percentage of subjects with one or more TEAEs for FEC cohort (not by individual drug agent)
- number and percentage of subjects with one or more procedure-related TEAEs for INT230-6 monotherapy treatments (all monotherapy cohorts combined)
- number and percentage of subjects with one or more related TEAEs for DEC and DEC2 cohorts (not by individual drug agent)
- number and percentage of subjects with one or more related TEAEs for FEC cohort (not by individual drug agent)
- number and percentage of subjects with one or more severe (Grade 3 or above) TEAEs

- number and percentage of subjects with one or more severe (Grade 3 or above) INT230-6 monotherapy treatment-related TEAEs (all monotherapy cohorts combined)
- number and percentage of subjects with one or more severe (Grade 3 or above) related TEAEs for DEC and DEC2 cohorts (not by individual drug agent)
- number and percentage of subjects with one or more severe (Grade 3 or above) related TEAEs for FEC cohort (not by individual drug agent)
- number and percentage of subjects with one or more serious adverse events (SAEs)
- number and percentage of subjects with one or more INT230-6 monotherapy-related SAEs (all monotherapy cohorts combined)
- number and percentage of subjects with one or more related SAEs for DEC and DEC2 cohorts
- number and percentage of subjects with one or more related SAEs (for FEC cohort)
- number of deaths (if any)
- number and percentage of subjects with one or more TEAEs resulting in discontinuation from the study

The frequency and percentage of TEAEs by SOC and PT for each treatment will be tabulated. The frequency and percentage of TEAEs by SOC/PT by maximum severity (Grade 1 - 5) will be presented by treatment. The frequency and percentage of Related TEAEs and of All TEAEs (related or unrelated) by PT and by maximum severity will be presented for the following cohorts:

- Overall Monotherapy
- Monotherapy Cohorts A1/B1/EA/EC
- Monotherapy Cohorts EC2/EC3
- Combination Pembrolizumab Cohorts DEC/DEC2
- Combination Ipilimumab Cohort FEC
- Monotherapy Sarcoma Subjects
- Combination Ipilimumab Cohort FEC Sarcoma Subjects
- Note:Sarcoma includes chordoma.

The number and percentage of TEAEs by SOC/PT considered related to study drug will be summarized. Number and percentage of subjects experiencing Grade 3 or higher TEAEs by SOC/PT will be summarized. Number and percentage of subjects experiencing Serious TEAEs by SOC/PT will be summarized. The frequency and percentage of TEAEs that lead to study discontinuation will be presented. If a subject moves from monotherapy to combination therapy treatment, the summary adverse events will be calculated based on the treatment at the time of the event.

A listing of all AEs data sorted by subject, including the verbatim term, MedDRA SOC and preferred term, duration of AE (calculated as Stop Date – Start Date + 1), Outcome, Severity, Relationship to Study Drug, Relationship to Dosing Procedure, Action Taken, Subject Discontinued Y/N, DLT Y/N, and SAE criteria, if relevant, will be provided. Additionally, individual AE records of SAEs, any deaths occurring during the study, AEs that led to discontinuation, Grade \geq 3 AEs, and DLTs will be listed separately.

